# **REVISION HISTORY**

Rev.	Change By	Description of Change	Rationale for Change	
0	[name]	Initial draft	Draft for FDA pre-sub	
1	[name]	Initial release	New	

# LIST OF ABBREVIATIONS

Abbreviation	Definition
AE	Adverse event
DD	Device deficiencies
SAE	Serious adverse event
CFR	Code of Federal Regulations
eCRF	Electronic case report form
EDC	Electronic data capture
ERP	Enterprise resource planning
DSM	Digital Study Model
FDA	Food and Drug Administration
GCP	Good Clinical Practice
HIPAA	Health Insurance Portability and Accountability Act
IC	Informed Consent
ICH	International Conference on Harmonization
IP	Investigational Product (equivalent with Investigational device)
IRB	Institutional Review Board
NSR	Non-significant risk
PAR	Peer Assessment Rating
CoCR	Center of Clinical Research
US	United States

# PROTOCOL SYNOPSIS

TITLE	A Prospective, multi-center Clinical Study to Support Substantial Equivalence of Safety and Effectiveness of Nighttime Aligners (worn 10-12 hours day or night)				
DESIGN	Multi-site, two-armed, prospective, controlled clinical study				
STUDY LOCATION	United States				
SUBJECT POPULATION	Permanent dentition (i.e., all second molars), ages 12 and up				
SAMPLE SIZE	The study will enroll up to 100 subjects [50 per treatment arm] to have a minimum of 23 fully evaluable subjects per treatment arm at end of treatment				
NUMBER OF SITES	Up to 15 investigational sites				
STUDY DURATION	18 months, inclusive of enrollment period, where typical treatment duration is 6-8 months				
TEST	Treatment arm 1 – Test group Nighttime Aligners (worn 10-12 hours per day or night)				
CONTROL	Treatment arm 2 – Control group Daytime Aligners (worn 20-22 hours day/night)				
OBJECTIVE	This clinical study is designed to provide Straight Smile, LLC and Dentsply Sirona data to support substantial equivalence, including safety and efficacy, of wearing Nighttime Aligners for 10-12 continuous hours per day (or night). The expressed movements demonstrated by the Nighttime Aligners (investigational/test group) will be compared to the expressed movements demonstrated by the Daytime Aligners (control group), which are worn for 20-22-hours per day/night.				
CLINICAL STUDY PROCEDURE	The flowchart below provides an overview of the clinical study. For visit-specific procedures, see section 8: Visit and procedure plan.				

	Test arm (Nighttime Aligners) Transformed Aligners) Control arm (Daytime Aligners) Transformed Aligners) Transformed Aligners (Transformed Aligners) Transformed Aligners (Transformed Aligners) Transformed Aligners (Transformed Aligners) Follow-up visits Conducted every 4d visit Optional Conducted every 4d visit Optional Treatment visit - Refinement visit - Treatment final Treatment period (2-8 months) Study duration, including enrollment period (approximatey 18 months in total)
EFFECTIVENESS ASSESSMENTS	Efficacy of Nighttime Aligners (worn 10-12 hours per day or night) will be assessed by demonstrating no statistically significant difference between expressed tooth movement versus programmed tooth movement at the end of treatment when compared to the Daytime aligners (worn 20-22 hours day/night). Quantification and comparison of expressed and programmed tooth movements will be conducted using Peer Assessment Rating (PAR) index to measure orthodontic treatment need and outcome, using the built-in weighted PAR analysis tool of 3Shape Ortho System software.
SAFETY ASSESSMENTS	The primary safety endpoint of the study will be the incidence of (device or dental) related AEs associated with the planned investigational treatment, as well as the occurrence of SAEs. Additionally, safety will be assessed through a post-treatment questionnaire administered to the subject asking about subject perceived comfort during treatment. Results will be quantified using a visual analogue scale. Both numerical values and a Wong Baker face scale will be used.
INCLUSION CRITERIA	
 
For inclusion in this clinical study subjects must meet all of the following criteria: 
 
Subject willing to participate in the clinical study and able to understand the content of the clinical study.
 
 
 
Subject must have permanent dentition (i.e. all second molars).
 
Subject must be 12 years of age or older.
 
Subject must be able to provide and sign consent for themselves, without requiring consent to be given by a legally authorized representative. Parental consent is also required for all participants who are not of the legal age to provide consent themselves (based on participant state of residence).
 
The subject requires correction of teeth without planned extrusive movements on either or both arches.
 

	
 
The subject has no greater than 5 mm of crowding and/or spacing (based on estimation by Investigator).
 

	
 
The subject does not require planned correction of molar tooth positions, posterior bite or molar classic relationship corrections. Subjects with Class II or Class III malocclusions requiring posterior bite / class correction are not eligible.
 

	
 
Subjects without prior orthodontic treatment within the past 18 months.
 

	9. Subjects who are periodontally stable.
	10. Subjects without a known history of plastic allergies.
	11. Subjects who have not had or do not require tooth extractions in preparation for orthodontic treatment with aligners.
	12. Subjects with a treatment plan that does not include the use of elastics.
	Any of the following is regarded as a criterion for exclusion from the clinical study:
	
 
Unlikely to be able to comply with clinical study procedures according to Investigator's judgement.
 

	2. Unable or unwilling to return for follow-up visits.
	3. Previous enrolment in the present clinical study.
	
 
Involvement in the planning and conduct of the clinical study (applies to both Sponsor personnel and the clinical study site)
 

	

Participation in another clinical study that may interfere with the present clinical study.

EXCLUSION CRITERIA	

Subjects who have active carries, where there is no plan to correct them prior to the start of aligner therapy.

	
 
Other dental or clinical pathologies, which in the judgment of the Investigator, deem the candidates inappropriate for participation in the study (e.g. clinically significant periodontal disease or gingivitis, interproximal decay, etc.).
 

	
 
The subject require interproximal reduction or attachments to obtain a corrected malocclusion.
 

	
 
In addition to the criteria listed above, this product is contraindicated for use in adult and adolescent subjects presenting with the following dental conditions:
 

	Active periodontal disease
	Severe open bite or severe overjet

Tooth malocclusion requiring surgical correction
Subject with mixed dentition

 
Subject with a skeletally narrow jaw
 

 
Dental prosthetics/implants or significant number of missing teeth
 

 
Known pregnancy, pregnancy tests will be performed as per local requirements.
 

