# 4.2 Number of Subjects

The study shall prospectively enroll up to 100 subjects (50 per treatment arm) on a convenience basis, with a minimum of 50 eligible subjects per treatment arm. A minimum of 23 fully evaluable, compliant, and viable subjects completing treatment in each study treatment arm is required.

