# 9.3 **Primary Efficacy Endpoint**

The primary effectiveness endpoint is the comparison between the treatment groups of the quantification of actual vs planned tooth movements using weighted Peer Assessment Rating (PAR) index.

• Planned percentage reduction in PAR Score (Planned Improvement of Malocclusion [PIM])

In addition comparison between treatment groups will also be performed for:

- Actual percentage reduction in PAR Score (Actual Improvement of Malocclusion [AIM])
- Percentage of Accuracy of Outcome

Quantification and comparison of expressed and programmed tooth movements will be conducted using to measure orthodontic treatment need and outcome, the built-in weighted PAR analysis tool of 3Shape Ortho System software (K152086).

- 9.3.1 The weighted PAR scores for each Digital Study Model (DSM) would be compared as follows:
  - Planned percentage reduction in PAR Score (Planned Improvement of Malocclusion [PIM]) = PAR Score TS- PAR Score TP / PAR Score TS \* 100
  - Actual percentage reduction in PAR Score (Actual Improvement of Malocclusion [AIM]) = PAR Score TS- PAR Score TF / PAR Score TS \* 100
  - Percentage of Accuracy of Outcome = 100% [(|PIM -AIM|/|AIM|) \*100%]

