#### 12.1 Statistical Sample Size and Power (provided as an example)

12.1.1 The current study is a controlled prospective study to determine the expressed movements demonstrated by investigational device, Nighttime Aligners for 10-12 continous hours per day/night compared to the control group, Daytime Aligners, which are worn for 20-22 hours per day.

**CONFIDENTIAL:** The information in this study protocol is strictly confidential and is available for review to Investigators, study center personnel, the ethics committee, and the health authorities. It will not be disclosed to third parties without written authorization from the Sponsor, except to obtain informed consent from persons receiving the study treatment. Once the protocol is signed, its terms are binding for all parties.

12.1.2 Sample size calculations for this study were determined using statistical software Minitab to ensure proper powering. The desired sample size per arm is 23 based on power calculations previously developed by Dentsply Sirona. The desired level of power is 90%. The desired confidence is 95% (p <0.05). Calculations are based on a standard deviation of 1, a power value of 0.9 and a detected difference of 1. The calculation also assumes a 2-sided, alpha = 0.05 level of significance.

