#### 12.2 Data Analysis

- 12.2.1 The Sponsor and Investigators are not blinded to the study data during the conduct of the trial, and may at periodic intervals analyze the data to assess study progress.
- 12.2.2 If nothing else is stated, descriptive statistics will be given for each variable in the clinical study and p-values may be complemented by confidence intervals as appropriate. When using the terminology descriptive statistics, it is meant that the number of subjects (N), mean, median, standard deviation (Sd), minimum (Min) and maximum (Max) values will be presented for continuous data and frequencies and percentages for categorical data.

- 12.2.3 All tooth movement data analyses will be performed using 3Shape Ortho System (K152086).
- 12.2.4 Three .stl files from each subject would be used for the analysis:
  - A pre-treatment STL file (TS) would be generated by scanning subject's pre-treatment intraoral scan taken before the start of treatment.
  - A planned or programmed STL (TP) file would be obtained from Archform Orthodontic Software System (K213916) after planned or programmed tooth movements have been made based on the treatment plan finalized by the digital lab and study Investigators.
  - The actual post-treatment STL file (TF) would be generated by scanning subject's post-treatment intraoral scan at the end of treatment.
- 12.2.5 Each STL file would convert into a Digital Study Model within the 3Shape Ortho System software to standardize the analysis.
- 12.2.6 Each DSM would be segmented using the "auto segmentation tool" of the software to demarcate each tooth separately.
- 12.2.7 This would be followed by Peer Assessment Rating (PAR) index to measure orthodontic treatment need and outcome (Richmond, 1992). This would be done using the built-in weighted PAR analysis tool of 3Shape Ortho System software. The PAR index will be performed by an external evaluator.
- 12.2.8 The weightage for each component of the PAR index would be set as: maxillary and mandibular anterior segment alignment x 1; buccal occlusion x 1; overjet x 6; overbite x 2; centerline x 4; following the ABO guidelines. The weighted PAR scores for each DSM would be compared as follows:

The PAR Score values for  $T_S$ ,  $T_P$ , and  $T_F$  will be transferred to the eCRF and the following will be calculated:

- Planned percentage reduction in PAR Score (Planned Improvement of Malocclusion [PIM]) = PAR Score TS- PAR Score TP / PAR Score TS \* 100

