- Actual percentage reduction in PAR Score (Actual Improvement of Malocclusion [AIM]) = PAR Score TS- PAR Score TF / PAR Score TS \* 100
- Percentage of Accuracy of Outcome = 100% [(|PIM AIM|/|AIM|) \*100%]

Statistical analysis comparing the two treatment groups using the Wilcoxon rank sum test will pe performed. A two-sided p-value below

5% will be regarded as statistically significant. The null hypothesis of the study is that there is no difference between the two groups.

- 12.2.9 Additional comparisons between treatment groups may be performed and p-values presented using the Wilcoxon rank sum test. Wilcoxon signed rank test may be used for analysis within treatment groups over time.
- 12.2.10 Calculation of Spearman's rank correlation coefficients will be performed to elucidate the relationships between the accuracy of outcome with treatment duration, number of aligners, subject pain levels, and overall subject and doctor satisfaction for each group.
- 12.2.11 All methods used in this clinical study have been previously published and reviewed (Griffith 2021, Grünheid 2022). All data in this clinical study will be analyzed by an independent contractor to remove bias. Any adjustments or modifications to these methods will be duly documented and reported.

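### Efficacy is judged by the absence of a significant difference, with no margin or confidence-interval rule, so the planned test cannot support the equivalence aim

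*Combined protocol and SAP*

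**What the plan says.** The synopsis objective is to provide "data to support substantial equivalence, including safety and efficacy, of wearing Nighttime Aligners for 10-12 continuous hours per day (or night". Under Effectiveness Assessments, the synopsis gives its efficacy criterion: "demonstrating no statistically significant difference between expressed tooth movement versus programmed tooth movement at the end of treatment when compared to the Daytime aligners".

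The body of the protocol sets no other criterion. Sections 1.1 and 9.3 speak only of a comparison between groups. Section 12.2.8 specifies a Wilcoxon rank sum test, significant if the two-sided p-value is below 5%, and states: "The null hypothesis of the study is that there is no difference between the two groups". Section 12.2.2 says that "p-values may be complemented by confidence intervals as appropriate", without giving a level, a bound or a use for them.

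Section 12.1.2 gives 23 per arm: "Calculations are based on a standard deviation of 1, a power value of 0.9 and a detected difference of 1", two-sided alpha 0.05. Its heading marks the calculation as an example, and no unit or endpoint is attached to the SD or the difference. Section 4.2 allows up to 50 enrolled per arm and adds: "A minimum of 23 fully evaluable, compliant, and viable subjects completing treatment in each study treatment arm is required".

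The measure bulleted directly under the primary endpoint in section 9.3 is "Planned percentage reduction in PAR Score (Planned Improvement of Malocclusion [PIM"). Actual improvement (AIM) and accuracy of outcome are listed there as additional comparisons.

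**The concern.** A two-sided test of no difference can produce evidence that the arms differ. It cannot produce evidence that they are alike, because a non-significant p-value is also what a small or noisy study gives when the arms do differ. Treating it as the efficacy result reverses the burden of proof: imprecision counts in favour of the device.

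That matters here for three reasons. The result is intended to support clearance. A deficit is plausible on the protocol's own account, since section 7.1.1 lists teeth shifting while the aligner is out as a risk made more likely by reduced wear. And the plan allows a wide range of evaluable numbers, from 50 down to 23 per arm.

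A reader could build an interval from the descriptive statistics but would have no prespecified margin to judge it against. Section 12.2.1 leaves the sponsor and investigators unblinded and free to analyse data periodically, so a margin chosen later would carry little weight.

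**Working it through.** **Inputs from the documents.** Two-sided alpha 0.05, power 0.90, SD 1, difference 1, 23 per arm (12.1.2); at most 50 enrolled and at least 23 evaluable per arm (4.2); Wilcoxon rank sum test (12.2.8).

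**Assumptions.** The documents give no SD in PAR units and no margin, so deficits and margins below are in SD units. Outcomes are taken as normal, on a measure that includes the post-treatment score.

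**1. The plan's own figure.** The normal approximation is n = 2(z₀.₉₇₅ + z₀.₉₀)² × (SD/difference)² = 2(1.960 + 1.282)² = 21.0, rounded up to 22. With the two-sample t-test (noncentral t), power is 0.8997 at 22 and 0.9125 at 23. So 23 is reproduced, as the size for detecting a 1 SD difference.

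**2. Chance of meeting the synopsis criterion.** Simulated probability that the Wilcoxon p-value is 0.05 or more (40,000 runs per setting, continuity-corrected):

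| True deficit of Nighttime | 23 per arm | 50 per arm |
|---|---|---|
| 0 | 0.953 | 0.951 |
| 0.25 SD | 0.876 | 0.776 |
| 0.5 SD | 0.646 | 0.329 |
| 0.6 SD | 0.513 | 0.179 |
| 0.65 SD | 0.455 | 0.118 |
| 0.75 SD | 0.326 | 0.047 |
| 1 SD | 0.108 | 0.003 |

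With no true difference, sample size makes no difference. With any of these deficits, fewer subjects raise the chance. At 23 per arm it exceeds one half for deficits up to about 0.6 SD.

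**3. What a non-significant result leaves open.** The 95% CI half-width is t₀.₉₇₅,₂ₙ₋₂ × √(2/n) SD.
- n = 23: 2.015 × 0.295 = 0.59 SD
- n = 50: 1.984 × 0.200 = 0.40 SD

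An observed deficit just short of significance is about one half-width. Its interval then reaches about 2 × 0.594 = 1.19 SD worse at 23 per arm, and 2 × 0.397 = 0.79 SD worse at 50.

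**4. What a margin-based design would deliver.** Non-inferiority, one-sided 2.5%, true difference 0:

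| Quantity | 23 per arm | 50 per arm |
|---|---|---|
| Power, 0.5 SD margin, t-based | 0.38 | 0.70 |
| Power, 0.5 SD margin, rank-based interval (simulated) | 0.36 | 0.68 |
| Smallest margin with 90% power, t-based | 0.98 SD | 0.66 SD |
| Smallest margin with 90% power, rank-based | about 1.01 SD | about 0.67 SD |

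For 90% power at 0.5 SD, the normal approximation gives 2(3.242/0.5)² = 84.1, or 85 per arm. The t-test needs 86 and the rank-based interval about 90. All exceed the 50 enrolled.

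For two-sided equivalence with a 0.5 SD margin and zero true difference, power using the 95% CI is 0.005 at 23 and 0.39 at 50; using the 90% CI it is 0.07 and 0.60.

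**5. The measure.** PIM is the reduction from the pre-treatment score (TS) to the planned score (TP), as a percentage of TS. The post-treatment score (TF) does not enter. A margin on PIM would compare treatment plans, not results.

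**The case against.** Four points can be made for the plan.

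- **The criterion rests on one synopsis sentence.** Section 2.2.2 restates the objective without the equivalence wording, and 12.2.8 never says that a non-significant p-value is success. Both are true, but the body offers no other criterion, and the null in 12.2.8 fits the synopsis. The synopsis wording is therefore the only rule available.
- **Substantial equivalence is a regulatory term.** It need not mean a formal two-sided equivalence test. That is correct, and non-inferiority could serve, but it too needs a margin and an interval rule.
- **The sample size is not shown to be wrong.** If 1 SD were justified as a margin, 23 per arm would give about 91% non-inferiority power (t-based). This stands. The defect is the missing margin and rule; whether 23 is enough depends on the margin. The plan does not call its difference of 1 a margin, give it a unit or justify it clinically.
- **The probabilities do not describe PIM.** They apply to a post-treatment measure, because a deficit in achieved movement does not enter PIM at all. That limit is accepted. The synopsis criterion concerns expressed against programmed movement, which does need the post-treatment score. Normality is also doubtful for percentage measures, especially accuracy, which divides by AIM.

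**Conclusion.** The concern holds, and it must be fixed before the data are analysed. As written, the plan lets a failure to reject a no-difference null count as efficacy in support of substantial equivalence. If Nighttime were truly 0.5 SD worse, that conclusion would follow about one time in three with 50 evaluable per arm and nearly two times in three with 23.

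The exact probabilities depend on normal outcomes and on deficits assumed in SD units. The logical defect depends on neither. The documents do not allow a margin to be derived on any PAR scale, so no claim is made that 23 or 50 per arm is too few for every margin.

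**What to change.** 1. In the synopsis and 12.2.8, replace the criterion with a non-inferiority hypothesis on one named PAR measure that includes the post-treatment score, and align 9.3 with it. AIM is one candidate, although alone it does not compare actual with planned. AIM minus PIM in percentage points does, and avoids dividing by AIM; being signed, it credits exceeding the plan and lets overshoot offset undershoot, so that choice needs a stated reason. PIM should not be used.
2. Prespecify a clinically justified margin in that measure's units.
3. Conclude non-inferiority only if the lower limit of the two-sided 95% CI for Nighttime minus Daytime, scored so that higher is better, lies above minus the margin. A Hodges-Lehmann interval keeps the rank-based approach. State that a non-significant Wilcoxon p-value alone supports no efficacy conclusion.
4. If two-sided equivalence is preferred, say whether a 90% or 95% CI is used and give the matching power.
5. Restate 12.1.2 with an SD in the measure's units, the margin, and the power at 23 and at 50 evaluable per arm.

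**Cost.** Wording, a margin justification and a less favourable power statement; no extra measurements. Power at 50 assumes no losses. If the justified margin is tighter than about 0.66 SD, 90% power is out of reach within the 100-subject cap. The sponsor would then report the lower power and limit the conclusion, or raise the cap.

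These changes do not deal with convenience enrolment, the absence of any described random allocation, or the focus on compliant completers. Those need separate attention before an interval that clears the margin can be read as a treatment comparison.

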# 7. RISKS AND BENEFITS OF PARTICIPATION

#### 7.1 **Risks**

- 7.1.1 The Sponsor has not identified any additional risks by participation in this clinical study. However, there are some risks that have an increased probability of occurrence with a reduced wear time aligner regimen including:
  - Reduced wear time causes teeth to shift while aligner is not worn; treatment takes longer than expected → Treatment Delay
  - Only wearing aligners for 10-12 hours per day can lead to greater subject discomfort when aligners are worn → Subject Discomfort
- 7.1.2 Additionally, there are risks associated with orthodontic treatment in general, including:
  - Discomfort: There may be some discomfort due to wearing an aligner for the first time, as the mouth is very sensitive. As the teeth move, often some discomfort is to be expected, however this usually wears off in a couple of days after each aligner tray

change. Aligners may cause irritation to the surrounding cheeks and lips.

- Allergy: Although rare, some people may be allergic to the plastic in aligners. If the subject knows that they have a plastic allergy or sensitivity, they should notify the Investigator prior to starting aligner therapy. Subject with known allergies to plastic materials are not eligible to participate in this clinical study. If an allergy to the aligner occurs, the Sponsor and/or the Investigator may recommend that treatment be paused and continued using alternative methods.
- Cavities: The surface of teeth may become weaker, and may have more cavities. Excellent oral hygiene will help to prevent this from happening during treatment.
- Resorption: The roots of teeth may become shorter or weaker during treatment. The Sponsor and/or the Investigator may recommend that treatment be paused if this process called root resorption occurs.
- Tooth movement not tracking according to the prescribed treatment plan: This can be caused by several factors; the top factor being subject compliance in wearing aligners the required number of hours per day/night. Treatment time may take longer than expected, or final outcomes may be different than what was planned when aligners are not worn as prescribed.
- X-ray: Standard procedures will be used i.e., all attempts to limit X-ray exposure will be made during the clinical study, including proper shielding.

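### The efficacy conclusion rests only on a non-significant between-arm test; no within-arm result is tied to it, so two arms that fail alike pass as often as two that succeed

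*Combined protocol and SAP*

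**What the plan says.** The Effectiveness Assessments entry of the synopsis is the only place that says how efficacy will be concluded: by "demonstrating no statistically significant difference between expressed tooth movement versus programmed tooth movement at the end of treatment when compared to the Daytime aligners".

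The sections that carry this out are comparative. Section 1.1 sets the primary efficacy objective as a comparison between groups. Section 9.3 says "The primary effectiveness endpoint is the comparison between the treatment groups of the quantification of actual vs planned tooth movements"; it lists planned improvement (PIM) first and then adds AIM and Percentage of Accuracy with the words "In addition comparison between treatment groups will also be performed for". Section 12.2.8 provides for "Statistical analysis comparing the two treatment groups using the Wilcoxon rank sum test" at a two-sided 5% level and adds: "The null hypothesis of the study is that there is no difference between the two groups".

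Two provisions bear on absolute performance. Section 12.2.2 gives descriptive statistics for each variable by default, which covers AIM and accuracy. Section 12.2.9 says "Wilcoxon signed rank test may be used for analysis within treatment groups over time". Neither is linked to the efficacy conclusion. The documents set no minimum AIM, minimum accuracy or performance goal, and do not require the Daytime arm to have performed as expected.

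**The concern.** The rule has one input, the contrast between arms. It cannot separate a study in which both regimens delivered the plan from one in which neither did. The second case would be worded as efficacy of an uncleared regimen.

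This differs from the missing equivalence margin. Two arms that fall short together differ by about zero on AIM, so a non-inferiority margin on AIM would also be met.

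Some shared shortfall is conceivable. Section 7.1.2 says several factors can stop teeth tracking to plan, "the top factor being subject compliance in wearing aligners the required number of hours per day/night". Both arms also use the same plastic (6.1.1), dentist network (8.1.1) and digital lab (8.2.3).

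**Working it through.** **1. The plan's own figure.** Section 12.1.2 gives SD 1, difference 1, two-sided alpha 0.05, power 90% and 23 per arm. The normal approximation is 2 × (1.960 + 1.282)² / 1² = 21.0, rounded up to 22. The noncentral-t calculation gives power 0.8997 at 22 and 0.9125 at 23. The plan's 23 is reproduced. It is a calculation for detecting a difference and has no bearing on absolute performance.

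**2. Pass rate when the arms are alike.** For one level-alpha test on identical distributions, P(non-significant) = 1 − 0.05 = 95%. Simulation of the Wilcoxon rank sum test gives 95.3% at n = 23 and 95.1% at n = 50 per arm.

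**3. The same at different levels of performance.** The documents give no PAR distributions, so these means are assumptions (PIM mean 75%). Entries are the percentage non-significant at n = 23.

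| True state in both arms | PIM | AIM | Accuracy |
|---|---|---|---|
| Good movement (mean AIM 70%) | 95.3 | 94.5 | 95.1 |
| Poor movement (mean AIM 10%) | 95.2 | 95.0 | 95.1 |
| No movement, scoring noise only | 95.3 | 95.1 | 95.5 |

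At n = 50 every entry is about 95%. Three side points:
- PIM uses only the baseline and planned models, so a test on PIM cannot register failure to move teeth.
- If every AIM were exactly 0, the AIM test gives p = 1 and accuracy is undefined, because |AIM| is its denominator.
- If all three comparisons had to be non-significant, the pass rate would be about 86–88% (0.95³ = 0.857 if independent).

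**4. Adding a signed-rank test of TS against TF in each arm, one-sided 2.5%.** With no movement, both arms pass by chance with probability at most about 0.025² = 0.0006, so the combined rule passes 0.1% or less.

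For partial expression the assumptions are: mean baseline PAR 10 to 18, planned PAR about 30% of baseline (PIM about 70%), 2-point scoring noise, SD of expressed fraction 0.15–0.20, and n = 23 to 50.

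| True expression of plan, both arms | Between-arm rule alone | With signed-rank test in each arm |
|---|---|---|
| 0% | about 95% | 0.1% or less |
| 20% | about 95% | about 26% to 95% |
| 50% or more | about 95% | under 1 percentage point lower |

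The wide range at 20% follows from signal against noise. The true fall is 0.2 × 0.7 × 10 = 1.4 points at mean baseline PAR 10 and 0.2 × 0.7 × 18 = 2.5 points at 18. The noise SD of a difference of two scores is 2 × √2 = 2.8. The low end is baseline 10 with n = 23; the high end is baseline 18 with n = 50.

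**5. A stricter floor, AIM above k × PIM in each arm.** With k = 0.5 and n = 23, the pass rate is about 94% at 80% expression, 71% at 70% and 11% at 60% (mean baseline PAR 18). It is about 69% at 80% expression if mean baseline PAR is 10.

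**The case against.** **The 95% is only 1 − alpha.** This stands. The figure says nothing about how likely shared failure is. It also assumes identical arms, whereas enrolment is on a convenience basis (section 4) and no randomisation is described, so case-mix differences could lower it.

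**Absolute results will be visible.** This stands too. A reader might infer that the optional signed-rank test is the only analysis showing absolute effect. Section 12.2.2 does not support that: AIM is measured against baseline and accuracy against plan, and both are summarised by default. What remains is that those summaries do not bear on the conclusion.

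**Complete failure is remote.** A reader might infer that the documents point to likely joint failure. They do not. The Daytime Aligners are cleared and have been marketed since 2019 (2.1.2). The required minimum counts compliant completers (4.2), compliance and tracking are reviewed every 4–6 weeks (8.8.1), and completion requires the investigator to decide that a retainer can be ordered (8.9.3). A comparative design is also natural for substantial equivalence. None of this shows that the control worked in this particular sample.

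**A margin might catch it.** On AIM it would not. On accuracy it can: with an illustrative 20-point margin and no movement, accuracy passes only about 4% of the time, because AIM near zero inflates its spread. The statement about margins is therefore limited to AIM.

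**Conclusion.** The point holds as a gap in assay sensitivity. With identical arms and one test, the rule concludes efficacy about 95% of the time whatever the level of tooth movement. That figure needs no PAR assumption; the effect of the fix does.

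The signed-rank requirement closes the no-movement case and costs almost nothing at 50% expression or more. At 20% expression it still passes about 26–95% of trials, so it should not be presented as protection against partial shared failure.

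A reader might go further and hold that a per-arm floor of k × PIM is needed and nearly free. The documents give no basis for any k, and step 5 shows that such a floor can fail studies in which both arms truly exceed it. It is an option for the sponsor, not part of the required change.

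**What to change.** 1. In 12.2.9, change the within-group signed-rank test from 'may' to 'will' be used.
2. In the synopsis and 12.2.8, add wording such as:

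> In addition to the between-arm criterion, efficacy will be concluded only if a one-sided 2.5% Wilcoxon signed-rank test shows TF PAR below TS PAR in each arm. If the Daytime arm does not meet this requirement, the comparison will be reported as uninformative rather than supportive.

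3. Report AIM and AIM/PIM for each arm, with confidence intervals, beside the efficacy conclusion.
4. If the sponsor also wants a floor of k × PIM, fix k before final scans are scored, since 12.2.1 leaves the sponsor unblinded and free to analyse data periodically. Show its pass rate over a range of baseline PAR and expression.

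Items 1 to 3 use PAR scores already collected and need no extra subjects, visits or readings. Under the stated assumptions the added chance of failing is under 1 percentage point at true expression of 50% or more. Item 4 carries the larger loss shown in step 5.
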